### ***3.4 Subject Selection and Enrollment Considerations***

#### ***3.5.1 Inclusion Criteria***

- 1) healthy persons between the ages of 20 and 90
- 2) persons six weeks post stroke between the ages of 20 and 90
- 2) person with enough shoulder, elbow, wrist, and hand movement to actively interact with the video games

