## Home Based Virtual Rehabilitation for upper extremity

**Title of Project:**

**Principal Investigator:**

**[name] PT PhD**

**Funding Source(s):**

**NIDILRR #90RE5021-01-00**

**NIH NICHD #1R15HD095403-01A1**

### 1. Purpose/Specific Aims

The overarching aim of this study is to provide a mechanism for patients to engage in progressive motor practice for a meaningful time period. We aim to improve on the positive outcomes found in our work on patients in the chronic phase and the pilot work being done on patients in the acute in-patient phase post stroke to determine whether we can further improve functional recovery using a home based system.

Aim 1: Evaluate compliance with Home-Based Virtually Simulated hand/arm gaming activities and two computer game groups, one with motivation enhanced (ME) simulations and one with non-enhanced (MnE) versions, as compared to compliance with Standard hand/arm home Exercises (HBSE). Hypothesis: Participants in the ME and MnE group will show significant compliance as compared to the control group (HBSE) and the ME group will be superior to the MnE group.

Primary Outcome Measures: For the HBVS group, 1) time on task will be measured by the daily computer file time stamp and 2) amount of moving time will be measured by the actual movement time recorded by the games. For the computer games groups 1) time on task will be measured by recording start and stop time of practice in a notebook and 2) amount of moving time will be measured by commercially available activity monitors.

Aim 2: Evaluate the effectiveness of home-based virtually simulated hand/arm gaming activities (HBVS) for individuals with stroke as compared to a program of standard hand/arm home exercises (HBSE). Hypothesis: Participants completing HBVS training will exhibit significantly improved clinical, kinematic and neurophysiological outcomes as compared to the control group (HBSE).

Primary Outcome Measures for Aim 2: Wolf Motor Function Test, Upper Extremity Fugl-Meyer Assessment of Sensorimotor Recovery after Stroke, Action Research Arm Test, Perception of System Questionnaire, the Stroke Impact Scale, Kinematics, Cortical mapping.

Aim 3: Evaluate the impact of the motivation enhancements designed into computer games to provide a more enjoyable training experience. Hypothesis: Enjoyment of the games will be a more valid predictor of compliance than personal factors.

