## **3. Research Design and Methods**

This study will be a single blind randomized controlled trial. Subjects will be blinded to the purpose of the study. All outcome measures will be performed by a therapist blinded to group assignment. A controlled trial will be utilized to determine the additive effect of presenting rehabilitation activities in a virtual environment as compared to standard upper extremity exercise. We will randomize subjects to treatment and control groups using a computerized random number generator.

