### ***3.3 Sample Size Justification***

In this pilot study we will seek sufficient power to detect a clinically significant difference in the Wolf score changes in these two pre-planned, primary comparisons. To evaluate these effects of training, we will assume a power level of .8 and a significance level of 0.05. With presumed correlation among repeated measures of 0.1 and effect size of 0.3, we will need a sample size of 25 subjects in each of the three groups (HBVS, ME and MnE) to observe a significant effect for the first comparison (G\*Power, version 3.1.5). Although we will screen for patients with homogeneous impairments, by its nature stroke is an extremely variable condition. Due to possible subject attrition, we will use a total of 30 subjects in each of the two groups.

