#### ***3.5.3 Subject Recruitment***

Subjects will be recruited through flyers, stroke support groups, and clinician referrals. We will assume that approximately 15-20% of the population will satisfy our inclusion criteria based on our previous experience with upper extremity rehabilitation in this population. Hence we will approach 300 persons.

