### **4.2 Dependent Variables or Outcome Measures**

All subjects will come to our lab and complete a quality of life questionnaire (Stroke Impact Scale) [4] and undergo clinical and kinematic testing immediately pre and post training as well as at 1 and 6 months post training. Additionally they will complete a perception of the system questionnaire [5] after training is completed.

Clinical Measures. The main clinical outcome will be the Wolf Motor Function Test [6] because it is a balanced test of arm and hand use [7, 8]. The secondary measures will be the Upper Extremity Fugl-Meyer Assessment[9], the Action Research Arm test[10], and Kinematic/Kinetic Measures. To explore the mechanism of improvement, changes in kinematics and kinetics of the hand and arm will be used to elucidate recovery of impairment. Two types of kinematic data will be collected; 1) data obtained from the patient's daily performance during the training and 2) data collected during the 4 testing

periods. Data obtained from the patient's daily gaming performance during the training will include duration of motor activity, hand opening and closing range of motion, pronation and supination range of motion, maximum fractionation (a measure of finger individuation), hand opening velocity, hand trajectory smoothness, game duration and game score.

Data collected during the 4 testing periods includes computer-based outcome measures and the Real-World Reach to Grasp Test. There are four computer based outcome measures in this data set. 1) Maximum Finger Opening is collected using a CyberGlove™ (Immersion, USA) (2) Pinch Force Tracking Error measures the ability to control active finger extension and flexion to modulate their pinch grip force to control a cursor to track a sine wave. (3) Maximum Pinch Force is measured as the maximum force a subject can exert on a force sensor held between their paretic thumb and index finger and, (4) Figure 8 Tracking Error measures forearm and shoulder control needed to trace a horizontal figure 8 shape while the arm is in a supported horizontal position[11] (5) Max finger extension and abduction (collected using a CyberGlove) (6)Maximum supination with hand open, measured with an Optitrack system. (7) Maximum pronation with hand open, measured with an Optitrack system (8) Maximum MCP flexion with PIP and DIP extension measured with an Optitrack system.

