The Kinematic Reach-Grasp Test analyzes the kinematics of everyday movements involving grasping and manipulating real-world household objects and will be used to measure changes in real-world function. The Reach-Grasp Test will be administered to both the hemiparetic and non-hemiparetic upper extremity at all assessment time points. Subjects will sit in a chair and reach for objects placed 20 cm from the hand starting position. The subjects will be instructed to grasp the objects from the table and place it onto a 10 cm high platform located 5 cm to the right of the object. Subjects will be required to have all five fingertips touch the object at the time of the grasp[12].

In an attempt to expand our understanding of the motivation and adherence to the autonomous home rehabilitation program, we will perform an in depth qualitative analysis focusing on subjects' unique perceptions and understandings of their participation in the proposed rehabilitation program. Using a Grounded Theory approach, data collection and analysis will follow these steps: 1) A trained interviewer will ask open-ended questions in a telephone interview conducted after follow up testing, allowing participants to reflect on and describe their experiences. 2) Investigators will read participants' narratives to develop a general sense of the subjects' experiences and attitudes toward the rehabilitation program. 3) Investigators will identify emerging narrative themes in participants' experiences and attitudes toward the program. 4) Finally, an iterative coding process will be used to refine initial findings and synthesize these themes.

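### Protocol inclusion criterion 1 makes healthy persons eligible, and no Protocol rule keeps them out of the randomised groups, although the Protocol's aims and the SAP's criteria presuppose stroke

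*Protocol*

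**What the plan says.** Protocol 3.5.1 lists as its first inclusion criterion "healthy persons between the ages of 20 and 90" and, as a separate item, "persons six weeks post stroke between the ages of 20 and 90". The remaining item asks for enough arm and hand movement to play the games. The four exclusions in 3.5.2 concern severe weakness, severe tone, attention and vision.

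Protocol section 3 states the allocation rule: "We will randomize subjects to treatment and control groups using a computerized random number generator". It does not limit this to people with stroke. Protocol section 5 gives a repeated-measures analysis of variance by therapy type and test occasion, and defines no analysis set. Protocol 3.3 asks for 25 subjects per group, raised to 30 for attrition.

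Other Protocol text takes stroke for granted. Aim 2 concerns individuals with stroke. Section 3.3 says: "Although we will screen for patients with homogeneous impairments, by its nature stroke is an extremely variable condition". Section 4.2 has every subject complete the Stroke Impact Scale, measures pinch force on the paretic side, and has the Reach-Grasp Test "administered to both the hemiparetic and non-hemiparetic upper extremity at all assessment time points".

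The SAP, under Subjects in Aim 1, recruits 30 persons with chronic stroke and requires unilateral stroke and a Fugl-Meyer score of 30 to 60 out of 66.

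**The concern.** A person cannot be both healthy and post stroke, so the two items can only be read as alternatives. A healthy adult in the age range meets the movement criterion easily and meets none of the exclusions. Followed literally, the Protocol therefore makes that person eligible, randomises them, and counts them toward the group total.

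The Wolf Motor Function Test, the Fugl-Meyer and the Action Research Arm Test measure function or impairment that a healthy person has not lost. Each healthy person randomised takes a place that the sample size assigns to a patient, and contributes a treatment effect near zero on these outcomes. The estimated difference between arms moves toward zero and power falls. The argument applies to the motor outcomes. For the compliance outcome (duration of motor activity), the documents give no basis for saying which way healthy persons would move the comparison.

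**Working it through.** **1. Is there a Protocol rule that excludes healthy persons?**

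- Inclusion (3.5.1): admits them by name.
- Exclusion (3.5.2): no item applies to a healthy adult.
- Randomisation (section 3): covers subjects without restriction.
- Analysis (section 5): no restricted analysis set.
- Recruitment (3.5.3): "Subjects will be recruited through flyers, stroke support groups, and clinician referrals". Flyers are not limited to people with stroke.
- A separate reference cohort: no purpose, number, visit schedule or analysis is given anywhere.

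The aims, sample size text and assessments presuppose stroke, but none of them is a rule for admitting, allocating or analysing a person.

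**2. Reproduce the planned sample size.** Inputs from Protocol 3.3: power 0.80, alpha 0.05, effect size 0.3 (taken as Cohen's f, the metric G*Power uses for analysis of variance), correlation 0.1. For the between-groups test with k groups, m occasions and N subjects in total:

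λ = f² × N × m / [1 + (m − 1)ρ], with k − 1 and N − k degrees of freedom.

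With k = 2, m = 2 and N = 50: λ = 0.09 × 50 × 2 / 1.1 = 8.18, and power is 0.800. So 25 per group reproduces. At 30 per group, power is 0.869. The values k = 2 and m = 2 are inferred, since the section does not state them. At alpha 0.05, k = 3 with m = 2 would give 21 per group, and k = 2 with m = 4 would give 16.

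**3. Put in a healthy share h.** The documents give none, so h is an assumption. If a share h of each arm has no treatment effect and the SD is unchanged, f becomes 0.3 × (1 − h), and the sample needed grows by about 1/(1 − h)².

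| Assumed h | f | Power at 25 per group | Power at 30 per group | n per group for 80% | 1/(1 − h)² |
|---|---|---|---|---|---|
| 0% | 0.30 | 80.0% | 86.9% | 25 | 1.00 |
| 10% | 0.27 | 71.3% | 79.2% | 31 | 1.23 |
| 20% | 0.24 | 61.1% | 69.3% | 39 | 1.56 |
| 30% | 0.21 | 50.1% | 57.8% | 50 | 2.04 |

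**4. Relax the SD assumption.** For two equal groups d = 2f, so f = 0.3 is d = 0.6. Suppose that healthy persons' change scores do not vary at all and equal the control mean. The average within-arm variance is then (1 − h)(1 + h d²/2).

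- h = 20%: variance 0.8 × (1 + 0.2 × 0.36/2) = 0.829, SD 0.910. Effective d = 0.48/0.910 = 0.527, so f = 0.264. In the formula of step 2, power at 25 per group is about 69%. The inflation in n is (0.6/0.527)² = 1.30, against 1.56 with the SD unchanged.
- h = 10%: variance 0.9 × (1 + 0.1 × 0.36/2) = 0.916, SD 0.957. Effective d = 0.54/0.957 = 0.564, so f = 0.282. Power is about 75%.

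**5. Vary the test.** For the group-by-occasion interaction with k = 2 and m = 4, which is closer to the analysis in Protocol section 5, power at 25 per group is 97.1% with no healthy persons, 93.0% at 10% and 85.5% at 20% (SD unchanged). The direction is the same, but the loss is smaller because this version starts with power to spare.

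**6. Compare with the recruitment yield.** Protocol 3.5.3 expects 15 to 20% of 300 persons approached to qualify: 0.15 × 300 = 45 and 0.20 × 300 = 60. The upper figure equals 2 × 30. A yield that low fits an impaired population, not one in which healthy adults qualify. It also leaves no evident room for an additional healthy cohort.

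**The case against.** The strongest reply is that nobody intends to randomise healthy persons. The aims, the sample size text, the paretic-limb assessments and the 15 to 20% yield all describe a stroke population. Having every subject complete the Stroke Impact Scale suggests that a subject here means a person with stroke. The healthy-persons line may be left over, or may refer to people giving reference values. As evidence of intent, this stands.

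A reader might go further than the documents allow in two ways.

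- **That nothing anywhere excludes healthy persons.** This is not so. The SAP's requirement of unilateral stroke shuts them out of the set that it randomises. That does not fully repair the Protocol, because the SAP describes a different trial: 30 subjects in two arms, enhanced against unenhanced games, aged 25 to 85. It does not clearly govern the Protocol's groups, which include a standard-exercise control.
- **That the trial will lose a known amount of power.** No document gives a healthy share or says that any will be enrolled. The percentages above show what would follow from assumed shares, and they depend on the SD and on the test.

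The reference-group explanation is possible, but it has to be supplied by the reader. Intent that must be inferred from other sections does not replace an eligibility rule, and the eligibility list is what decides who can enter.

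**Conclusion.** The point holds as a defect in the Protocol's eligibility rule and as a conflict between that rule, the rest of the Protocol, and the SAP. It does not show that the sponsor chose to randomise healthy persons.

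Dilution of the motor-outcome difference is conditional on healthy persons actually being randomised. Its direction follows from their having little or no deficit to recover. Its size is illustrative. In the calculation that reproduces 25 per group, an assumed 10% healthy lowers power from 80% to between 71% (SD unchanged) and 75% (no variation in healthy change). An assumed 20% lowers it to between 61% and 69%. These figures rest on an equal healthy share in both arms, no treatment effect in healthy persons, and two groups and two occasions inferred from the match. With healthy persons kept out, the stated 25 per group is unaffected by this point.

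Because the remedy is so small, this should be corrected even though the size cannot be established.

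**What to change.** Either delete criterion 1 from Protocol 3.5.1, or move healthy persons to a separate paragraph that states their purpose and number and says that they are not randomised, not counted in the 30 per group, and not part of any arm comparison. In the second case, add a sentence to Protocol section 5 limiting the analysed set to randomised persons with stroke.

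Then reconcile eligibility between the two documents. The Protocol has ages 20 to 90, six weeks post stroke and no impairment range. The SAP has ages 25 to 85, chronic unilateral stroke and Fugl-Meyer 30 to 60. State which set applies to which randomised groups.

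The first change is one line and the second a short paragraph. Neither alters the sample size, visits or outcomes. If anyone has already been enrolled under criterion 1, report how many and whether they were randomised.

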#### ***3.5.2 Exclusion Criteria***

- 1) person with severe arm weakness and cannot move the arm enough to interact with the video games
- 2) person with severe increase in tone of their weak arm
- 3) person with difficulty following instructions or paying attention to computer video games for at least ten minutes,
- 4) person with visual problems that make it difficult for them to interact with an entire computer screen

#### ***3.5.3 Subject Recruitment***

Subjects will be recruited through flyers, stroke support groups, and clinician referrals. We will assume that approximately 15-20% of the population will satisfy our inclusion criteria based on our previous experience with upper extremity rehabilitation in this population. Hence we will approach 300 persons.

#### ***3.5.4 Consent Procedures***

Example: The study will be explained to the potential subject by the study staff, the consent will be read, and their questions will be answered. If s/he wishes to enroll, the

subject will sign the consent form. The study staff obtaining consent will also sign and date the consent form, and a copy will be given to the subject sought from each prospective subject or the subject's legally authorized representative, in accordance with federal & state law and institutional policy. If the study staff member performing the consent process identifies issues suggesting that the prospective subject may not be capable of participating in the consent process due to dementia, a Folstein Mini Mental Status will be performed. Prospective subjects screening positive for dementia will not be included in the study.

### ***3.5.5 Subject Costs and Compensation***

There are no costs for the subjects. The subjects will be paid 100\$ at each of the retention tests.

## **4. Study Variables**

### ***4.1 Independent Variables or Interventions***

The two **computer game groups, Motivation Enhanced (ME) and Motivation Non-Enhanced (MnE)** will use the NJIT- Home Virtual Rehabilitation System (HoVRS) to play a series of computer games developed to practice movement of the hand and fingers. Subjects will first come into our lab, perform pre-tests as well as a pre-intervention training session. Then a physical therapist and engineer will set up the apparatus in subject's home and will train them on how to use the system and play the games in their home during the first week. The physical therapist and engineer will be in contact with subjects throughout the training and will visit subjects' homes as needed if problems are encountered. Additionally, the system allows the therapist to remotely monitor each day's activity.

#### ***4.1.1 Device Description***

NJIT HoVRS has two sub-systems to deliver home-based training: 1) a patient based platform to provide the training and 2) a server based online data logging and reporting system. In the patient's home, a cross platform virtual reality training application runs video games (developed in the Unity 3D game engine using the language C#) on their home computer.

#### ***4.1.11 Hardware***

The Leap Motion Controller (LMC) a commercially developed infrared tracking device developed for home video game control is used to capture motion of the hand and arm movement without requiring wearable sensors. The device's USB controller reads the sensor data into its own local memory and performs any necessary resolution adjustments. This data is then streamed via USB to the Leap Motion image API. From there, we programmed the system to feed tracking data into virtual reality activities by calling the Leap Motion API.

If the patient's arm is weak and he/she cannot support the hand against gravity above the Leap Motion Controller, the Armon™ Edero, a commercially available, spring-based arm support, will be provided to the subject (Figure 1). The Edero provides 12 different levels of passive

support allowing it to accommodate a wide range of patient sizes and strength levels. It requires a single setting that can be provided during the patient's initial evaluation

#### **4.1.1.2 Software**

Patients will either use their own home computer or will be provided with a computer if needed. A user-friendly GUI interface lists all of the training activities allowing patients to choose which activity they want to begin with using just one mouse click. Currently twelve games have been developed, each one designed to focus on training a specific hand or arm movement such as wrist rotation or finger individuation. All games are downloadable via HoVRS website.

The **video home exercise** group will be taught a progression of home exercises for their hand and arm. These exercises will be taught to them using web-based movies that they will view on a computer screen. Subjects will first come into our lab, perform pre-tests as well as a pre-intervention training session. The therapist will then work with the subjects in their home and visit them once or twice in the first week to ensure that they are independent exercising with the videos. The video exercise activities will include hand opening activities, reaching and grasping different sized objects, individual finger movements, and forearm rotation activities chosen to ensure the trained movements are similar to the ones addressed by the computer games.

#### **4.1.1.2 Software**

Patients will either use their own home computer or will be provided with a computer if needed. A user-friendly GUI interface lists all of the video home exercises allowing patients to choose which activity they want to begin with using just one mouse click. Currently twelve exercises have been developed, each one designed to focus on training a specific hand or arm movement such as wrist rotation or finger individuation. All games are downloadable via the HoVRS website.

### **4.2 Dependent Variables or Outcome Measures**

All subjects will come to our lab and complete a quality of life questionnaire (Stroke Impact Scale) [4] and undergo clinical and kinematic testing immediately pre and post training as well as at 1 and 6 months post training. Additionally they will complete a perception of the system questionnaire [5] after training is completed.

Clinical Measures. The main clinical outcome will be the Wolf Motor Function Test [6] because it is a balanced test of arm and hand use [7, 8]. The secondary measures will be the Upper Extremity Fugl-Meyer Assessment[9], the Action Research Arm test[10], and Kinematic/Kinetic Measures. To explore the mechanism of improvement, changes in kinematics and kinetics of the hand and arm will be used to elucidate recovery of impairment. Two types of kinematic data will be collected; 1) data obtained from the patient's daily performance during the training and 2) data collected during the 4 testing

periods. Data obtained from the patient's daily gaming performance during the training will include duration of motor activity, hand opening and closing range of motion, pronation and supination range of motion, maximum fractionation (a measure of finger individuation), hand opening velocity, hand trajectory smoothness, game duration and game score.

Data collected during the 4 testing periods includes computer-based outcome measures and the Real-World Reach to Grasp Test. There are four computer based outcome measures in this data set. 1) Maximum Finger Opening is collected using a CyberGlove™ (Immersion, USA) (2) Pinch Force Tracking Error measures the ability to control active finger extension and flexion to modulate their pinch grip force to control a cursor to track a sine wave. (3) Maximum Pinch Force is measured as the maximum force a subject can exert on a force sensor held between their paretic thumb and index finger and, (4) Figure 8 Tracking Error measures forearm and shoulder control needed to trace a horizontal figure 8 shape while the arm is in a supported horizontal position[11] (5) Max finger extension and abduction (collected using a CyberGlove) (6)Maximum supination with hand open, measured with an Optitrack system. (7) Maximum pronation with hand open, measured with an Optitrack system (8) Maximum MCP flexion with PIP and DIP extension measured with an Optitrack system.

The Kinematic Reach-Grasp Test analyzes the kinematics of everyday movements involving grasping and manipulating real-world household objects and will be used to measure changes in real-world function. The Reach-Grasp Test will be administered to both the hemiparetic and non-hemiparetic upper extremity at all assessment time points. Subjects will sit in a chair and reach for objects placed 20 cm from the hand starting position. The subjects will be instructed to grasp the objects from the table and place it onto a 10 cm high platform located 5 cm to the right of the object. Subjects will be required to have all five fingertips touch the object at the time of the grasp[12].

In an attempt to expand our understanding of the motivation and adherence to the autonomous home rehabilitation program, we will perform an in depth qualitative analysis focusing on subjects' unique perceptions and understandings of their participation in the proposed rehabilitation program. Using a Grounded Theory approach, data collection and analysis will follow these steps: 1) A trained interviewer will ask open-ended questions in a telephone interview conducted after follow up testing, allowing participants to reflect on and describe their experiences. 2) Investigators will read participants' narratives to develop a general sense of the subjects' experiences and attitudes toward the rehabilitation program. 3) Investigators will identify emerging narrative themes in participants' experiences and attitudes toward the program. 4) Finally, an iterative coding process will be used to refine initial findings and synthesize these themes.

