### **5. Data Handling and Statistical Analysis**

All efforts will be made to keep subjects' personal information confidential. All subject names will be removed from the data and the data will be tagged using a coded ID number.

Demographic, clinical outcome and survey data will first be recorded on paper. All kinematic and computerized performance data will be collected on computer. These computer files will be identified by the coded subject ID number. All data will be transferred to an Excel spreadsheet with subjects identified by this same ID number. Spreadsheets will be stored on a drive that is password protected. Data will only be accessible to study staff and will be retained for seven years. The link between subject identity and subject ID number will be destroyed when data collection is completed.

Our primary outcome measures will be the WMFT (Aim 2) and the duration of motor activity (measure of compliance, Aim 1). The primary outcome measures and all secondary outcome measures described above will be subjected to a repeated measured analysis of variance, with between-group factors Therapy Type (Virtual Simulations (VS), Standard Exercise (SE)) and within-group factor Test (Before, Post, One Month retention, Six Months Retention). Our post-hoc analyses of the Therapy Type by Test interaction effects will focus on the Month 1 versus Month 6 comparison. We will be quantifying training effects by comparing group means as well as by percent change in performance, and by comparing the recovery curves obtained from Tests 1-4. All clinical outcomes used are well established measures of upper extremity functional recovery with published minimum clinically important differences which we will use to evaluate the significance of our findings.

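### Protocol Sections 1, 4.2 and 5 disagree on whether kinematic outcomes are primary for Aim 2, Section 4.2 miscounts them, and the significance claim made on them has no stated error control

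*Protocol*

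**What the plan says.** **Status.** In Protocol Section 1, the Aim 2 hypothesis is that participants in the virtual training group "will exhibit significantly improved clinical, kinematic and neurophysiological outcomes as compared to the control group (HBSE". The list of primary outcome measures for Aim 2 in the same section includes a general entry for kinematics. Section 4.2 ranks them lower: "The secondary measures will be the Upper Extremity Fugl-Meyer Assessment[9], the Action Research Arm test[10], and Kinematic/Kinetic Measures". It then gives their purpose: "To explore the mechanism of improvement, changes in kinematics and kinetics of the hand and arm will be used to elucidate recovery of impairment". Section 5 names the WMFT as the primary outcome for Aim 2.

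**Number.** Section 4.2 says "Data collected during the 4 testing periods includes computer-based outcome measures and the Real-World Reach to Grasp Test". Of the computer-based set it says "There are four computer based outcome measures in this data set", but the numbered list runs on to "8) Maximum MCP flexion with PIP and DIP extension measured with an Optitrack system". The Reach-Grasp Test is described separately. It is done on both limbs at every assessment, and its analysis variables are not listed.

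**Analysis.** Section 5 states: "The primary outcome measures and all secondary outcome measures described above will be subjected to a repeated measured analysis of variance". The between-group factor is therapy type, and the other factor is the "within-group factor Test (Before, Post, One Month retention, Six Months Retention". The supplied Protocol text names no lead kinematic measure, no order of testing among the kinematic measures and no multiplicity adjustment. The 0.05 level appears only in Section 3.3, for the Wolf sample size, and its sidedness is not stated.

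**SAP.** Table 4 lists a different set of five kinematic/kinetic measures, so it does not settle the Protocol's count.

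**The concern.** Aim 2 makes a claim of statistical significance about a group of outcomes, but the Protocol does not fix their rank or their number, or say what result would count as meeting the claim. If kinematics are primary, as in Section 1, a set of eight or more tests with no allocation of alpha carries a confirmatory hypothesis. If they are secondary and mechanistic, as in Section 4.2, the Section 1 hypothesis promises more than the design intends to support. Under either reading, a report could present one significant kinematic result as confirming part of Aim 2, and the Protocol would give no basis for saying that it does not.

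**Working it through.** **1. Status, side by side.** Section 1: primary for Aim 2, with a significance hypothesis. Section 4.2: secondary, to explore mechanism. Section 5: WMFT is the Aim 2 primary, and secondary outcomes get the same ANOVA. Section 1 cannot be reconciled with the other two without a change of text.

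**2. Count.** Stated: 4. Numbered: 8. Reach-Grasp variables come on top, number unknown.

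**3. The plan's own figure.** The documents give no family-wise error rate. The nearest figure is 25 per group in Section 3.3 (effect size 0.3, taken as Cohen's f; correlation 0.1; alpha 0.05; power 0.8). The between-groups repeated-measures form, with noncentrality f²Nm/(1+(m−1)ρ), reproduces it for two groups and m = 2 measurements: 0.09 × 50 × 2 / 1.1 = 8.18, power 0.800 at N = 50. The 0.05 therefore belongs to one Wolf comparison. Using 0.05 for each kinematic test is an assumption. (The text speaks of three groups and plans four test times. That is a separate matter and does not affect what follows.)

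**4. Independent tests, no true effect.** Two-sided 0.05 is assumed for each measure, with one test per measure.
- Any false positive, eight measures: 1 − 0.95⁸ = 33.7%. Four measures: 1 − 0.95⁴ = 18.5%.
- A false positive in favour of virtual training (0.025 each), eight measures: 1 − 0.975⁸ = 18.3%. Four measures: 1 − 0.975⁴ = 9.6%.

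**5. Correlated tests.** The documents give no correlation between measures, so a range is used. For k equicorrelated normal statistics with c = 1.96:

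P(any) = 1 − ∫ [Φ((c − √ρ·u)/√(1−ρ)) − Φ((−c − √ρ·u)/√(1−ρ))]ᵏ φ(u) du

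The second Φ term is dropped for the benefit direction only.

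| ρ | 8, either direction | 8, benefit only | 4, either direction | 4, benefit only |
|---|---|---|---|---|
| 0 | 33.7% | 18.3% | 18.5% | 9.6% |
| 0.3 | 30.0% | 15.2% | 17.4% | 8.7% |
| 0.5 | 25.0% | 12.5% | 15.6% | 7.8% |
| 0.7 | 19.1% | 9.5% | 13.0% | 6.5% |
| 0.8 | 15.8% | 7.9% | 11.4% | 5.7% |
| 0.9 | 11.9% | 6.0% | 9.4% | 4.7% |

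A single measure gives 5% in either direction and 2.5% for benefit.

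**6. Check with the planned test.** With two groups and four test times, the therapy-by-test interaction has (2−1)(4−1) = 3 degrees of freedom. Simulating that F test on eight measures (25 per group, 4,000 runs) gave 33.0%, 26.4% and 16.8% at ρ = 0, 0.5 and 0.8. These are within 1.4 percentage points of the table. The F test has no sign, so the benefit-only columns are an approximation that treats each measure as one directional contrast.

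**7. What moves the range.** Measures 1 and 5 both record finger opening or extension with the CyberGlove, so full independence is an upper bound for these eight. In the other direction, the figures leave out the Reach-Grasp variables, the other ANOVA effects and the post-hoc tests. One further independent measure gives 1 − 0.95⁹ = 37.0%.

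**8. After a change.** One lead measure: 5%, or 2.5% for benefit. For an adjustment over eight, the first Holm threshold is 0.05/8 = 0.00625. Under independence the error is 1 − (1 − 0.00625)⁸ = 4.9%.

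**The case against.** The best defence is that the Protocol already ranks these outcomes. Section 5 makes the WMFT the Aim 2 primary, Section 4.2 calls kinematics secondary and gives them an exploratory purpose, and Section 3.3 describes a pilot study. On that view no adjustment is owed. A reader might infer that the kinematic measures carry no exploratory label at all; Section 4.2 does not support that. The defence protects the WMFT claim. It does not cover Section 1, which lists kinematics as primary and hypothesises a significant benefit.

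A reader might also infer that the Protocol accepts significance on any one measure as enough. It does not say so: the hypothesis refers to outcomes in the plural and gives no criterion. The any-one rule is a scenario used to size the problem.

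The four-versus-eight discrepancy looks like a count left unchanged when items were added: the conjunction stands before item 4, and items 5 to 8 follow. Section 5 takes in all secondary outcomes described, which covers all eight. The suggestion that the denominator could be picked afterwards is therefore weak. The count still needs correcting, because any adjustment depends on it.

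Finally, the SAP's Table 5 of planned comparisons is not in the supplied text, so the absence of an adjustment can be asserted for the Protocol only.

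**Conclusion.** The point holds as an inconsistency of status and count, with a significance claim attached that has no stated error control. If any one of eight significant results were taken as support, the chance of at least one false positive in either direction is about 16–34%. A reader might take that as the chance of falsely claiming a benefit, but it counts differences in both directions. For benefit, which is what Aim 2 hypothesises, the figure is about 8–18%, roughly three to seven times the 2.5% for one measure (7.9/2.5 = 3.2; 18.3/2.5 = 7.3). Both ranges assume two-sided 0.05 per test, one test per measure and correlation from 0.8 to 0; at 0.9 they fall to 11.9% and 6.0%. The WMFT analysis is not affected. What is at stake is the credibility of the kinematic part of Aim 2.

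**What to change.** 1. In Section 4.2, correct the stated count to the number of computer-based measures actually collected at the test sessions.
2. Reconcile Sections 1, 4.2 and 5 by removing the general kinematics entry from the Aim 2 primary list. Changing only Sections 4.2 and 5 would leave the conflict in place.
3. Choose one of two routes and write it into Section 5:
   - name one kinematic measure in advance to carry the Aim 2 kinematic claim, and label the rest, with the Reach-Grasp kinematics, exploratory (estimates with 95% confidence intervals, no significance claims); or
   - if claims on several measures are wanted, list the set in full and apply Holm across it.

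This is a change of wording and needs no new data or visits. The downside is that fewer kinematic results can be called significant. Under Holm, the smallest p-value among eight would have to reach 0.00625.
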